Among women scheduled to receive Gardasil, the second and third vaccine visit will occur two and six months following the initial baseline visit. Qualified staff and clinicians will conduct these study visits. After a negative urine-based pregnancy test, the visit will conclude with vaccination and monitoring for adverse events. All adverse events, serious and not serious, will be documented.

All participants will have blood collected at the 12, 24, and 36 month follow-up visits, either in a clinic or home setting (Table 2). For participants in the Cervarix group, blood also will be collected at a follow-up visit one month after vaccination. Each girl is expected to have five study visits, one for vaccination and four follow-up visits. Each woman is expected to have six study visits, three for vaccination and three for follow-up.

Table 2. Proposed study visits for the two groups.

	Visit type (months)						
Age	V00*	V01	V02*	V06*	V12	V24	V36
9-14 years	X	X			X	X	X
18-25 years	X		X	X	X	X	X

*Indicates vaccination visit

Throughout the duration of the trial, we will monitor plans for country-wide implementation of HPV vaccination, which will target fourth-grade girls (usually 10 year olds). At the time when the country begins vaccination, we will initiate procedures for ceasing enrollment of 9- and 10-year olds according to the SOP requested by the DSMB. Note, our recruitment plan for the younger cohort ensures that we will include 347 girls that will not be targeted by the national vaccination program.

Finally, if at 36-months the GMT for 1 dose at the group level is inferior to that of 3 doses, all 1-dose girls will be invited to receive the 2nd dose of Cervarix.

Selection of Study Vaccines

Both vaccines to be used in this study are licensed in the US and Costa Rica. As described, the bivalent HPV vaccine is produced by GSK (Cervarix®) and contains HPV 16 and 18 antigens, the quadrivalent vaccines is produced by Merck (Gardasil®) and additionally contain HPV 6 and 11 antigens. Besides the differences in HPV types included, the bivalent vaccine has a proprietary adjuvant called AS04, consisting of monophosphoryl lipid A (MPL) and aluminum hydroxide. MPL is a detoxified bacterial lipopolysaccharide which is a TLR-4 agonist involved in activation of innate and adaptive immune responses. The quadrivalent vaccine has aluminum hydrophosphate sulfate as adjuvant.

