If a woman meets the two- and six-month visit criteria to be vaccinated, she will proceed with vaccination. After vaccination, observation for 15 minutes will be completed and monitoring for adverse events performed as in the enrollment visit.

Active Follow-up of Both Groups (Months 1, 12, 24, and 36)

All participants will have follow-up visits every 12 months, and participants in the Cervarix group will have an additional visit one month after the vaccination. These visits will be conducted either in the home or a clinic setting. At each follow-up visit, the doctor or other qualified health professional will assess eligibility to complete the visit and collect updated HPV vaccination data. The 12-month visit for Gardasil group participants will include assessment of any occurrence of serious adverse event reactions or newly chronic conditions diagnosed after the final vaccination. Finally, blood will be collected from all willing participants. These visits can be completed at home.

Home Visits During Follow-up

All follow-up visits may be conducted at either the clinic or at home (at the convenience of the participant and/or her parent/guardian, as applicable), if an appropriate environment for performing blood collection is provided. The clinic team member who schedules the home visit will determine, based on an SOP created by the Investigators, whether the home setting is appropriate.

Procedures and data collection

Medical history

At the enrollment visit, we will conduct a complete medical history (and physical examination if considered necessary by the clinician evaluating the eligibility) to determine the participants' overall health status and eligibility for the study.

Among younger participants, the medical history will initially be completed with the participant's parent or guardian present to facilitate collection of information about any aspect

of her medical history with which the participant may not be familiar. After the first assessment of the medical history, the parent/guardian is asked to wait in the outer clinic area only if the participant is 12 years old or older. Then, the doctor will review the results of the pregnancy test.

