There is considerable accumulated data on the safety of these FDA- and EMA-approved vaccines. Given the design of the trial, the study will lack reference rates of occurrence of specific events among unvaccinated women. Nevertheless, we will monitor all trial participants for adverse events (AEs) at the clinic for at least 15 minutes after vaccination with appropriate medical treatment readily available in case of a rare anaphylactic reaction. Adverse events (AEs)

occurring during this period will be documented and followed to resolution. In case participants present non-serious expected adverse events like site reactions (mild pain), dizziness, or headache they will receive recommendations and Paracetamol will be available.

The consent and assent forms include a discussion of possible adverse events and will advise participants and their parents/guardians about what will happen if they experience an adverse event during the clinic visit. The consent and assent forms will also give guidance on how for participants to report adverse reactions that occur after the participant leaves the visit. The consent forms explain the study's insurance coverage and that, per Costa Rican Human Research Law, the study may pay for the care of conditions determined to be related to the study vaccines or procedures.

In addition, following each vaccination, participants will be told that they should report to study staff any serious problems they have in the month after each vaccine administration that require medical attention, whether they think the problem is related to vaccination or not.

Finally, participants will be actively queried at the study visit that follows each vaccine administration regarding SAEs that occurred after vaccination. Additionally, Cervarix group participants will be contacted at 6 months, either by phone or personally to inquire about vaccine reactions and to maintain contact to promote compliance with follow-up visits. In either case, the clinician will probe for adverse events by asking the participant whether she has been diagnosed with an illness, disabled for more than one day, or hospitalized since her last visit. These questions are included in the eligibility screener at the second and third vaccination visit, and the 12-month visit for the Gardasil Group, and in the six-month contact script for Cervarix group.

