For the full duration of the trial, AEs spontaneously reported by study participants will be documented. All deaths will be documented irrespective of timing between the occurrence of the event and vaccination.

All the adverse events, serious and not serious, reported by participants as part of active monitoring during the visit after vaccination completion (i.e., the 6-month phone contact for Cervarix group participants, and the 2-, 6- and -12-month visits for Gardasil group participants), or as part of passive monitoring throughout the duration of the study (i.e., reported spontaneously by the participant) will be documented. All events that are not resolved at the time of reporting will be followed up to document their resolution; if the SAE results in a chronic condition, it will be followed until medical management of the condition is documented. Should the event result in hospitalization, or otherwise require hospital record review according to the criteria of the Principal Investigator or designee, trained staff will review the medical records at the hospital, if necessary, and will extract relevant information to

clarify the evolution, diagnosis, treatment and resolution of the event. In a separate informed consent/assent form, participants and their parents/guardians, as applicable, will be asked to provide authorization for review of hospital charts if necessary.

Non-serious AEs directly related to study procedures other than the vaccine (e.g., blood collection) also will be documented and followed to resolution.

The Costa Rica Principal Investigator will report SAEs to the responsible regulatory authorities in Costa Rica, and to the NCI Principal Investigator. The reporting of AEs to regulatory entities in the United States will be the responsibility of the NCI Principal Investigator. Procedures for reporting AEs in the United States will be determined according to the NCI's Ethical Review Panel (ERP) guidance.

The Costa Rica Principal Investigator will report AEs to the Costa Rica IRB as stipulated in the regulation of the Human Subject Research Regulatory Act (Law 9234). Additionally, the Costa Rica Principal Investigator will report all AEs related to vaccination to the Pharmacovigilance office of the Costa Rica Minister of Health.

The DSMB will also monitor AEs for safety. The DSMB will review AEs according to their reporting and meeting schedule, as specified in the DSMB Charter.

Protocol Deviation Monitoring and Reporting

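### The protocol contradicts itself on whether girls are asked about adverse events at month 1; if they are not, the six-month question, as worded, skips the weeks after their only dose

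*Protocol*

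**What the plan says.** Four parts of the protocol bear on this.

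- **General rule** (*Expected Adverse Events and Adverse Event Monitoring and Reporting*): "participants will be actively queried at the study visit that follows each vaccine administration regarding SAEs that occurred after vaccination". It is not limited to one group. The next sentence adds a contact for girls: "Cervarix group participants will be contacted at 6 months, either by phone or personally to inquire about vaccine reactions". The probe, said to apply in either case, asks "whether she has been diagnosed with an illness, disabled for more than one day, or hospitalized since her last visit".
- **Where the questions are placed** (same paragraph, last sentence): for women, the second and third vaccination visits and the 12-month visit; for girls, "in the six-month contact script for Cervarix group". Month 1 is not listed.
- **Definition of active monitoring** (same section, further on): the visit after vaccination is complete is spelled out as "the 6-month phone contact for Cervarix group participants, and the 2-, 6- and -12-month visits for Gardasil group participants". Again, girls have no month-1 entry.
- **Visit schedule and content**: *Active Follow-up of Both Groups* says "participants in the Cervarix group will have an additional visit one month after the vaccination", and Table 2 in the *Overview* shows it as V01. The stated content of follow-up visits is a check of eligibility for the visit, an update on HPV vaccination, and blood. Adverse-event assessment is named only for the women's 12-month visit.

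**The concern.** One recall phrase serves both groups, but the visit schedules differ. For women, the scheduled visit before each query is a dosing visit, so a look-back to the last visit covers the time since that dose. For girls, a non-dosing visit falls between the only dose and the six-month contact. If month 1 carries no adverse-event questions, the six-month question starts about a month too late.

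At stake is the completeness of adverse-event data for the regimen under test, in the month for which participants are told to report serious problems. The DSMB reviews these data.

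**Working it through.** No power, sample-size or alpha figure is involved, and the plan states no figure to reproduce. The check sets each listed query against the preceding scheduled visit in Table 2, then sizes the possible gap.

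**Step 1. Look-back of each listed query**

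| Group | Query | Preceding scheduled visit | Dose given there? | Time since dose covered? |
|---|---|---|---|---|
| Women | V02 | V00 | Yes (first) | Yes |
| Women | V06 | V02 | Yes (second) | Yes |
| Women | V12 | V06 | Yes (third) | Yes |
| Girls | Six-month contact | V01 | No | No: V00 to V01 omitted |

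The women's rows assume that doses are given at their scheduled visits.

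**Step 2. The same check under the general rule.** If the probe is also asked at V01, its look-back there runs to V00, and the six-month look-back runs to V01. The two periods join with no gap. Whether there is a gap therefore depends on whether V01 carries the questions, and on that the protocol gives two answers.

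**Step 3. Girls exposed to the gap if V01 carries no questions.** Inputs: 520 to 620 girls (*Overview*); 10% assumed not to return at month 1 (*Power and Sample Size Considerations*).

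- Attending V01: 520 × 0.90 = 468; 620 × 0.90 = 558.
- Missing V01: 520 − 468 = 52; 620 − 558 = 62. Their last visit is enrollment, so the six-month question does cover the first month.

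**Step 4. Length of the gap.** Nominally one month. SAP section 3b accepts month-1 blood from day 14 to day 90. That is an analysis window, but if it approximates when V01 takes place, the gap is 14 to 90 days.

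**Step 5. Events in the gap.** The documents give no rate. Assuming that 0.5% to 2% of girls have a qualifying event in that period:

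- Low: 468 × 0.005 = 2.3.
- High: 558 × 0.02 = 11.2.

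That is about 2 to 11 events. The range follows entirely from the assumed rate.

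**The case against.** A reader might infer that the girls' first month is never actively asked about. The documents do not support that. The general rule covers both groups, the six-month contact is described as additional, and the probe applies to both occasions. Read that way, girls are asked at V01 and the wording works. The six-month contact is also meant to ask about vaccine reactions, which ties it to the dose rather than to the last visit. The contact script is not in the documents and may use a different start date from the protocol's summary.

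Nor do the documents support saying that the girls' event count will be too low, or that a planned comparison is biased. The first holds only if V01 carries no query. On the second, no objective and no SAP analysis compares safety between groups. Other capture exists: 15 minutes of observation, the instruction to report serious problems in the month after each dose, spontaneous reports throughout, documentation of all deaths, and a staffed contact service.

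Most of this stands, and it limits the point to a conflict in the text. It does not remove the conflict. The placement sentence, the definition of active monitoring and the description of visit content all leave out month 1, and staff following them would not ask then. A question about vaccine reactions is no full substitute: it can miss an illness that the girl or her parent does not attribute to the vaccine, whereas participants are told to report serious problems whatever they think the cause.

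**Conclusion.** The protocol is internally inconsistent on active adverse-event follow-up of girls, and first-month capture after the single dose is therefore not assured. If the operational statements govern, about 468 to 558 girls have a scripted recall period that omits nominally one month after vaccination. That period would rest on the 15-minute observation, spontaneous reports and a general question about vaccine reactions, while each women's query looks back to a scheduled dosing visit. If the general rule governs, there is no gap, but the three operational statements are wrong.

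The head count rests on the protocol's 10% non-attendance assumption. The 14 to 90 days rests on using the SAP blood window for visit timing. The 2 to 11 events rest on an assumed rate. The primary immunogenicity conclusion is not affected. The text should be corrected on either reading, and the correction is cheap.

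**What to change.** 1. Reconcile *Active Follow-up of Both Groups* with the three statements in the adverse-event section (general rule, placement of the questions, definition of active monitoring), so that all say whether the adverse-event questions are asked at V01.
2. In the adverse-event section and the six-month contact script, start the Cervarix group's recall period at the vaccination date (date of V00) instead of the last visit. This closes the gap whichever way item 1 is settled.
3. For the Gardasil group, anchor each query to the date of the most recent dose, so that coverage does not depend on which visits fall between.
4. If the contacts are already complete, report which wording and which visits were used, and state any resulting limitation on the girls' first-month adverse-event counts.

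The recall change is one phrase in the protocol and script, and the reconciliation is a matter of text. Neither needs a new visit or sample. The downside is a girls' recall period of about six months instead of about five.

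### The protocol promises an active safety question at the girls' 1-month visit, but its lists of where the questions are asked name only the 6-month contact for girls

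*Protocol*

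**What the plan says.** Three parts of the protocol bear on this.

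- **General commitment** (Expected Adverse Events and Adverse Event Monitoring and Reporting): "participants will be actively queried at the study visit that follows each vaccine administration regarding SAEs that occurred after vaccination". The next sentence presents the girls' 6-month contact as an extra: "Additionally, Cervarix group participants will be contacted at 6 months, either by phone or personally to inquire about vaccine reactions". The one after it covers both occasions: "In either case, the clinician will probe for adverse events by asking the participant whether she has been diagnosed with an illness".
- **Specific lists** (same section): "These questions are included in the eligibility screener at the second and third vaccination visit, and the 12-month visit for the Gardasil Group". The only place that this list gives for girls is "in the six-month contact script for Cervarix group". Further on, active monitoring is spelled out as the 2-, 6- and 12-month visits for women and, for girls, "the 6-month phone contact for Cervarix group participants".
- **Visit content** (Active Follow-up of Both Groups): "participants in the Cervarix group will have an additional visit one month after the vaccination". At each follow-up visit staff are to "assess eligibility to complete the visit and collect updated HPV vaccination data", and blood is drawn. An assessment of serious adverse events is named only for the Gardasil group's 12-month visit.

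Table 2 in the Overview shows month 1 as the girls' first visit after vaccination. It has no 6-month entry for them, and the Overview's count of five visits per girl does not include the 6-month contact.

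**The concern.** The general commitment reaches the girls' 1-month visit, but the operational passages leave it out. Forms and interview scripts would naturally be built from the specific lists, so the promised query may not be on the 1-month form.

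What is at stake is active safety capture in minors during the first month after vaccination. The protocol itself singles out that month by telling participants to report serious problems arising in it. Without a question at month 1, capture of those events rests on spontaneous report, or on recall at a 6-month contact that may be by telephone. That contact may not ask about the first month at all, depending on how its recall period is worded.

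**Working it through.** There is no planned figure to reproduce. The check sets the passages side by side and does arithmetic on nominal visit months.

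**1. Which visit follows the girls' vaccination?** Table 2 and the follow-up section both give month 1. The 6-month contact cannot be the visit meant: it is absent from Table 2, is not among the five counted visits, and is introduced as additional.

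**2. Where are the questions placed?**

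| Protocol text | Girls, month 1 | Girls, month 6 | Women |
|---|---|---|---|
| General commitment (adverse-event section) | implied | described as additional | visit after each dose |
| List of scripted questions (same section) | not named | named | second and third vaccination visits, month 12 |
| Definition of active monitoring (same section) | not named | named | months 2, 6, 12 |
| Follow-up visit content | not named | not a visit | month 12 |

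No text names the girls' 1-month visit as a place where the questions are asked.

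**3. Time from dose to next scripted query if the lists are followed** (query month minus dose month)

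- Girls, only dose: 6 − 0 = 6 months. Their next study visit is at 1 − 0 = 1 month, so the scripted query comes 6 − 1 = 5 months after that visit.
- Women, dose 1: 2 − 0 = 2 months.
- Women, dose 2: 6 − 2 = 4 months.
- Women, dose 3: 12 − 6 = 6 months.

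**4. What period does the probe cover?** As worded in the adverse-event section, it looks back to the participant's previous visit.

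- A girl who attended month 1 and is contacted at month 6 is asked about months 1 to 6. Months 0 to 1 are not covered.
- A girl who missed month 1 is asked about months 0 to 6.
- Women are asked about months 0 to 2, 2 to 6 and 6 to 12, with no gap.

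**5. How many girls?** Planned enrolment is 520 to 620. The sample-size section assumes that 10% miss the 1-month visit. On that assumption 0.90 × 520 = 468 to 0.90 × 620 = 558 girls would be seen at month 1 without a scripted safety question, if the lists are followed. The number of events missed cannot be estimated from the documents.

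**6. After the fix.** The girls' first query falls at 1 month instead of 6. Through month 6 they have two queries (months 1 and 6), as women do (months 2 and 6), instead of one. No statistical quantity changes.

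**The case against.** The strongest reply is that the query is already required. The general sentence covers the girls' 1-month visit, the 6-month contact is additional, and the probe applies on both occasions. On that reading the lists are merely incomplete. No script, screener or form is among the documents, so nothing shows that girls are not in fact asked at month 1. This stands as a limit: what can be shown is a conflict in the text, with a consequence only if the lists are what staff follow. It does not remove the conflict, because the definition of active monitoring is written as a complete statement and omits month 1.

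Existing safeguards also count. They include 15 minutes of observation, the instruction to report serious problems in the first month, a contact service staffed throughout, documentation of spontaneous reports and review by the data and safety monitoring board. The girl is also seen by a health professional at month 1. These apply whichever reading is right, but none is an active question about the first month.

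The explicit promise concerns serious events; the wider adverse-event wording comes from the probe sentence.

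A reader might infer that safety capture is unequal between the groups and that event frequencies are therefore not comparable. The documents do not support that. The first query does come later for girls than for women (6 against 2 months), but after the last dose the interval is 6 months in both groups, and each group has one scripted query per dose. The groups are non-randomized and differ in age, product and number of doses, so comparability would be limited in any case. No objective and no SAP analysis compares safety between them.

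**Conclusion.** The protocol contradicts itself on active safety questioning of girls. If the lists are followed, the first scripted query comes 6 months after the dose although the girls attend in person at 1 month. Read literally, the recall wording could leave the first month never actively asked about for those who attended month 1.

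This rests on nominal visit times and on protocol wording alone; the scripts actually used could show that the question was asked. The amendment log records that the 1-month visit was added in Version 1.3 for blood collection. That the safety text was not updated at that time is a plausible explanation, but only an inference.

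The point concerns safety data collection. The primary non-inferiority result, power and type I error are untouched. It is still worth acting on, because the participants are minors and both the visit and the questions already exist.

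**What to change.** Reconcile the follow-up visit section with the commitment, the script list and the definition of active monitoring in the adverse-event section:

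- Name the girls' 1-month visit as an active-monitoring visit in each of these places, and put the existing question set on its form. This carries out what the general commitment already promises.
- Keep the 6-month contact, and word its recall period as since vaccination so that the first month is covered even when the 1-month visit took place.

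The cost is a wording change to the protocol and forms and a few minutes per girl. No objective, endpoint or analysis changes.

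The documents give no enrolment dates, and the current protocol version is from March 2023, about four years after the 1-month visit was added, so those visits may already be complete. In that case, document what was asked at month 1 and what recall period was used at month 6, and describe the girls' first-month safety data accordingly.

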HPV neutralization is measured by SEAP-NA. Antibody levels measured by ELISA will be compared to neutralizing antibody levels measured by the pseudovirion-based neutralization assay, SEAP-NA. This nested study will select 36-month serum samples from a random set of 100 18-25 year old women who are HPV 16/18 seronegative at baseline and a random set of 100 9-14 year old girls who are HPV 16/18 seronegative at baseline, and then evaluate the HPV-16 and HPV-18 antibody levels in each of those 200 samples using both ELISA and SEAP-NA. For each HPV type, we will perform a Deming regression comparing log(ELISA) levels with log(SEAP) levels, where log(ELISA) is the dependent variable and log(SEAP) is the independent variable. We will consider ELISA as an acceptable assay for the primary endpoint if the 95% confidence intervals of the regression slope excludes $1-\Delta$ and $1+\Delta$ for both HPV types, with $\Delta = 0.3$. If the true slope is $b=0.9$, the variance of the measurement error for both log(ELISA) and log(SEAP) is $\sigma^2 = 0.4$, and the total variance of log(SEAP) = 1.9, then the power to achieve this serology objective is 0.94. Preliminary data suggests that $0.9 < b < 1$ and $0.10 < \sigma^2 < 0.45$. The power for other combinations of sample sizes, slopes, and variances are provided in Table 3. Note the power is significantly reduced if we consider each group of females separately. Furthermore, we will estimate the intra-assay measurement error by measuring 30 samples, 15 from 9-14 year old girls and 15 from 18-25 year old women, twice on each of the assays. **Therefore, for the purposes of the serology study, the total number of samples run on each assay will be 230.** If we do not achieve the serology objective, we will evaluate the data with partners at regulatory agencies to determine whether ELISA can be still be considered as an acceptable assay for measuring the primary endpoint.

Table 3: Power calculations. The table lists the power to demonstrate that the 95% confidence interval for the slope describing the relationship between ELISA and SEAP-NA measures, on the log scales, excludes 0.7 and 1.3 for the specified sample sizes (N = 50, 100, 150, or 200), slopes (b = 0.9, 1.0), and variances (σ^2 = 0.25, 0.45).

	b = 0.9			
	N = 50	N = 100	N = 150	N = 200
$\sigma^2 = 0.25$	0.54	0.92	>0.99	>0.99
$\sigma^2 = 0.45$	0.12	0.48	0.73	0.88
	b = 1			
	N = 50	N = 100	N = 150	N = 200
$\sigma^2 = 0.25$	0.85	>0.99	>0.99	>0.99

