HPV binding is measured by ELISA. The quantity of HPV16 and 18 IgG antibody response measured by VLP ELISA will be utilized to address immunogenicity endpoints. To further define the primary analytic cohort, HPV6 and HPV11 antibodies will be measured by VLP ELISA in a subset of participants to confirm, beyond self-report, that the according to protocol analytic cohort includes only girls who did not receive external HPV vaccination through the national program, which uses quadrivalent vaccine (HPV 6, 11, 16, 18). This will assure that girls in the single-dose HPV vaccination arm did not get additional doses.

HPV neutralization is measured by SEAP-NA. Antibodies levels measured by ELISA will be compared to neutralizing antibody levels measured by the pseudovirion-based neutralization assay, SEAP-NA. This nested study will select 24- month serum samples from a random set of 100 baseline seronegative 18-25 year old women and a random set of 100 baseline seronegative 9-14 year old girls, and then evaluate the HPV-16 and HPV-18 antibody levels in each of those 200 samples using both ELISA and SEAP-NA. For each HPV type, we will perform a Deming regression comparing $\log(\text{ELISA})$ levels with $\log(\text{SEAP})$ levels, where $\log(\text{ELISA})$ is the dependent variable and $\log(\text{SEAP})$ is the independent variable. We will confirm that ELISA is an acceptable assay for the primary endpoint if the 95% confidence intervals of the regression slope excludes $1-\Delta$ and $1+\Delta$ for both HPV types, with $\Delta = 0.3$. If that criterion is not achieved, then we will initiate a discussion with relevant parties to assess acceptability of the assay.

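### The ELISA acceptability rule is also met when the slope's 95% CI lies wholly outside 0.7 to 1.3 (minor; wrong as written)

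*Protocol*

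**What the plan says.** The protocol's Serology section plans a nested study of 200 sera, 100 from women and 100 from girls, measured by both assays: "For each HPV type, we will perform a Deming regression comparing log(ELISA) levels with log(SEAP) levels". The decision rule follows: "We will consider ELISA as an acceptable assay for the primary endpoint if the 95% confidence intervals of the regression slope excludes". The values that the interval has to exclude lie Δ = 0.3 either side of 1, so the limits are 0.7 and 1.3, and the rule has to be met for each of the two HPV types.

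SAP section 8 has the same rule, with the same two values: "We will confirm that ELISA is an acceptable assay for the primary endpoint if the 95% confidence intervals of the regression slope excludes". The Table 3 caption defines the event whose power is tabulated as "the 95% confidence interval for the slope describing the relationship between ELISA and SEAP-NA measures, on the log scales, excludes 0.7 and 1.3".

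Both documents provide a fallback, and in both it depends on failure. Protocol: "If we do not achieve the serology objective, we will evaluate the data with partners at regulatory agencies". SAP: "If that criterion is not achieved, then we will initiate a discussion with relevant parties to assess acceptability of the assay".

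The protocol's preliminary data put the slope between 0.9 and 1 and the error variance between 0.10 and 0.45.

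**The concern.** Excluding two points is not the same as lying between them. A 95% CI contains neither 0.7 nor 1.3 in three situations: it is inside the limits, wholly below 0.7, or wholly above 1.3. Only the first shows that the assays agree. The other two show that they do not, yet the written rule accepts them. No sentence in either document requires the CI to lie between the limits.

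The fallback does not repair this, because it begins only when the criterion is not met. A CI wholly outside the limits counts as meeting it, so the clearest evidence of disagreement would not start the planned discussion. One discordant HPV type is enough, since the other type would pass in the ordinary way.

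**Working it through.** **Inputs (protocol, Serology).** N = 200; total variance of log(SEAP) 1.9; error variance s² equal for the two assays (0.40 in the stated power, 0.10 to 0.45 in the preliminary data); limits 0.7 and 1.3; stated power 0.94 at slope b = 0.9.

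**1. Reproduce the stated power.** The large-sample variance of the Deming slope with error ratio 1 is

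Var = [1.9·s²·(1 + b²) − (b·s²)²] / [N·(1.9 − s²)²].

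At b = 0.9, s² = 0.40, N = 200: (1.9 × 0.40 × 1.81 − 0.36²) / (200 × 1.5²) = (1.3756 − 0.1296) / 450 = 0.00277, so SE = 0.0526.

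- P(CI inside the limits) = Φ((b − 0.7)/SE − 1.96) + Φ((1.3 − b)/SE − 1.96) − 1 = 0.967 per type. For two types taken as independent, 0.967² = 0.935, against 0.94 stated.
- The written rule adds P(CI wholly below 0.7) = Φ((0.7 − b)/SE − 1.96) and P(CI wholly above 1.3) = Φ((b − 1.3)/SE − 1.96). Both are practically 0 here, so the result is again 0.935.

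The same formula matches Table 3 to within about 0.01 under either reading. The largest difference between readings is 0.0001 (b = 0.9, s² = 0.45, N = 50: 0.1231 against 0.1232). The published power therefore cannot show which rule was meant.

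**2. Example intervals that pass as written.** At s² = 0.45, N = 200:

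- b = 0.5: SE = √[(1.06875 − 0.050625) / (200 × 1.45²)] = 0.049, so the CI is about 0.40 to 0.60.
- b = 1.6: SE = √[(3.0438 − 0.5184) / (200 × 1.45²)] = 0.0775, so the CI is about 1.45 to 1.75.

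**3. How often the written rule passes when the slope is discordant.** These slopes are assumed for illustration and are not in the documents. Simulation: true log(SEAP) normal with variance 1.9 − s², independent errors of variance s² on each assay, Deming slope with error ratio 1, CI = estimate ± 1.96 jackknife SE, N = 200, 20,000 runs per setting (Monte Carlo SE at most 0.0035). Pass probability per HPV type:

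| True slope | s² = 0.45 | s² = 0.40 | s² = 0.10 |
|---|---|---|---|
| 0.5 | 0.959 | 0.980 | 1.000 |
| 0.6 | 0.502 | 0.557 | 0.997 |
| 0.65 | 0.181 | 0.207 | 0.676 |
| 0.95 | 0.993 | 0.998 | 1.000 |
| 1.4 | 0.263 | 0.314 | 0.940 |
| 1.6 | 0.987 | 0.995 | 1.000 |

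At slopes 0.5, 0.6 and 1.6, none of the 20,000 runs had a CI inside the limits, so every pass there came from a CI wholly outside. At 0.9, 0.95 and 1.0, none had a CI wholly outside.

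**4. Both types (product of the two probabilities, independence assumed), at s² = 0.45 / 0.40 / 0.10.**

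- One type at 0.95, the other at 0.5: 0.993 × 0.959 = 0.95 / 0.98 / 1.00.
- One at 0.95, the other at 0.6: 0.50 / 0.56 / 0.997.
- One at 0.95, the other at 1.6: 0.98 / 0.99 / 1.00.
- Both at 0.5: 0.92 / 0.96 / 1.00. Both at 1.6: 0.97 / 0.99 / 1.00.
- Both at 0.65: 0.03 / 0.04 / 0.46. Both at 1.4: 0.07 / 0.10 / 0.88.

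If the CI must lie inside the limits, all of these are about 0.

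**5. At a limit.** For a true slope exactly at 0.7 or 1.3 (s² = 0.40, formula), the written rule passes a type with probability 0.05, against 0.025 when the CI must lie inside.

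**The case against.** The strongest reply is that the intent is plain. The limits are symmetric around 1, power is given only at slopes 0.9 and 1.0, and an analyst who saw a CI of 0.40 to 0.60 would hardly report agreement. The high pass probabilities mostly need a slope near 0.5 or 1.6, far from the preliminary range. With moderate discordance, such as 0.65 or 1.4, the written rule usually fails at the higher error variances, so the fallback would start. A failure leads only to a discussion, and the non-inferiority criteria (protocol, Analysis; SAP 7a) do not refer to this check.

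All of that stands, and it limits the importance of the point. It does not make the rule right. If the preliminary slope range could be taken as certain, the nested study would not be needed; it is there to test agreement for each type, and the wording fails exactly where disagreement is clearest. At the low end of the preliminary error variance (0.10), even a slope of 1.4 passes with probability 0.94 per type. A pre-specified rule for the primary-endpoint assay should not need interpreting once the slope is known.

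Two technical reservations also stand. The simulation gives 0.958 for both types at the protocol's power assumptions, where the formula gives 0.935, so the figures carry some approximation. Independence of the types is doubtful, because both are measured on the same sera. Neither changes the one-discordant-type result materially, since the concordant type passes about 0.99 of the time.

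**Conclusion.** The concern holds, as a minor point. Followed literally, the rule in the protocol, the Table 3 caption and SAP section 8 accepts ELISA when the slope CI lies wholly outside 0.7 to 1.3, and the fallback is then not triggered. At 200 samples, a slope of 0.5 passes with probability 0.96 to 1.00 per type and a slope of 1.6 with 0.99 to 1.00, against about 0 under the evident intention. These figures rest on assumed discordant slopes, the protocol's variance figures, normal data and equal error variances. The stated power and Table 3 are not in error. The defect has a practical consequence only if the true slope for at least one type is well outside 0.7 to 1.3, which the preliminary data do not suggest.

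**What to change.** In the protocol's Serology section and SAP section 8, replace the exclusion wording with a requirement that the 95% CI of the slope lie entirely within (1−Δ, 1+Δ), that is, lower limit above 0.7 and upper limit below 1.3, for both HPV types. Make the matching change in the Table 3 caption, and state that any other result triggers the fallback discussion.

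The cost is one phrase in three places. No new samples or data are needed. The 200 samples, the 0.94 power, Table 3 and the non-inferiority rules stay as they are.
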